#### Renal toxicity (mice and rats).

In mice, renal proximal tubular toxicity was observed following repeated oral administration of eltrombopag in a 2-year carcinogenicity study at 1.4-fold clinical exposure in ITP patients. Renal toxicity was not observed in mice in a 13-week study at a greater exposure (4.5-fold clinical exposure in ITP patients, respectively) than that achieved at the lowest dose in the 2-year study, suggesting that the renal effects are time-dependent. In rats, an increase in the incidence or severity of spontaneous, age-related chronic progressive nephropathy was observed at a similar exposure level, but not at lower exposures. The relationship of this finding to the renal effects observed in mice is unknown. No renal toxicity was observed following repeated oral administration to rats for 28 weeks or to dogs for 52 weeks at exposures up to 4.5- and 2.9-fold clinical exposure in ITP patients.

#### *Hepatotoxicity (mice, rats and dogs)*

In mice, rats and dogs, hepatocyte degeneration and/or necrosis, often accompanied by markedly increased serum liver enzymes, was observed following repeated oral administration of eltrombopag at exposures generally associated with morbidity and mortality. In rats and dogs, no treatment-related hepatic effects were observed after 28 or 52 weeks at exposures up to 4.5- or 2.9-fold clinical exposure in ITP patients.

#### Genotoxicity

The toxic potential of eltrombopag was also assessed in a battery of in vitro and in vivo genetic toxicology studies and the weight of evidence provided by these assessments suggests that eltrombopag does not pose a genotoxic risk in humans.

#### Carcinogenicity

Eltrombopag was not carcinogenic to mice or rats following 2-year carcinogenicity studies.

## Teratogenicity

Eltrombopag was not teratogenic in rats or rabbits and did not affect fertility in male rats or fertility, early embryonic development, embryofetal development, maternal

reproductive function, or development of offspring in female rats at non-maternally toxic doses. No effect on embryofetal development was observed in rabbits. At a maternally toxic dose in rats, treatment with eltrombopag was associated with embryolethality, a low incidence of cervical ribs (a non-teratogenic fetal variation) and reduced fetal body weight. In definitive juvenile toxicity studies in rats, eltrombopag was not associated with adverse effects. In vitro, eltrombopag was toxic in the presence of ultraviolet-A (UV-A) radiation, indicating a phototoxic response. However, there was no evidence of cutaneous phototoxicity in hairless mice or ocular phototoxicity in pigmented or albino mice or rats. Eltrombopag also showed evidence of photoclastogenicity in vitro that was associated with cytotoxic drug concentrations (15 to 29  $\mu$ g/mL) and high intensity UV exposure [30 minimal erythematous dose (MED)]. However, no evidence of photoclastogenicity was observed at a 2-fold higher concentration (58.4  $\mu$ g/mL) and UV exposure of ~15 MED. Eltrombopag did not adversely affect immune function in an immunotoxicity study in rats.

# Clinical Pharmacology (based on studies done in healthy subjects and subjects with hepatic impairment or renal impairment)

**Absorption:** Eltrombopag is absorbed with a peak concentration occurring 2 to 6 hours after oral administration. Based on urinary excretion and biotransformation products eliminated in feces, the oral absorption of drug-related material following administration of a single 75 mg solution dose was estimated to be at least 52%. In a clinical study, administration of a single 75 mg-dose of EPAG with a polyvalent cation-containing antacid (1,524 mg aluminum hydroxide, 1,425 mg magnesium carbonate, and sodium alginate) decreased plasma EPAG AUC0- $\infty$  and Cmax by 70%. The contribution of sodium alginate to this interaction is not known. An open-label, randomized, crossover study was conducted to assess the effect of food on the bioavailability of eltrombopag. A standard high-fat breakfast significantly decreased plasma eltrombopag AUC0- $\infty$  by approximately 59% and Cmax by 65% and delayed Tmax by 1 hour. The calcium content of this meal may have also contributed to this decrease in exposure.

**Distribution**: The concentration of EPAG in blood cells is approximately 50-79% of plasma concentrations based on a radiolabel study. In vitro studies suggest that eltrombopag is highly bound to human plasma proteins (>99%). Eltrombopag is not a substrate for p-glycoprotein (Pgp) or OATP1B1.

**Metabolism:** Absorbed eltrombopag is extensively metabolized, predominantly through pathways including cleavage, oxidation, and conjugation with glucuronic acid, glutathione, or cysteine. In a human radiolabel study, eltrombopag accounted for approximately 64% of plasma radiocarbon AUC0- $\infty$ . Metabolites due to glucuronidation and oxidation were also detected. In vitro studies suggest that CYP 1A2 and 2C8 are responsible for the

oxidative metabolism of eltrombopag. UGT1A1 and UGT1A3 are responsible for the glucuronidation of EPAG.

**Elimination:** The predominant route of eltrombopag excretion is via feces (59%) and urine (31%). Unchanged EPAG in feces accounts for approximately 20% of the dose; unchanged eltrombopag is not detectable in urine. The plasma elimination half-life of eltrombopag is approximately 21 to 32 hours in healthy subjects and 26-35 hours in ITP patients.

**Race**: Based on both non-compartment analysis and population pharmacokinetic analysis, plasma eltrombopag exposure was approximately 70% higher in some Asian subjects (East and South East Asian) with ITP as compared to non-Asian subjects who were predominantly Caucasian in these trials. In addition, the pharmacodynamic (PD) response to eltrombopag was qualitatively similar in the Asian subjects, but the absolute PD response was somewhat greater. An approximately 40% higher systemic EPAG exposure in healthy African-American subjects was noted in at least one clinical pharmacology study. The effect of African-American ethnicity on exposure and related safety and efficacy of eltrombopag has not been established.

**Gender**: Results from a population pharmacokinetic model suggest that males have a 27% greater apparent EPAG clearance than females, after adjustment for the body weight difference.

**Hepatic Impairment:** Plasma EPAG pharmacokinetics in subjects with mild, moderate, and severe hepatic impairment compared to healthy subjects was investigated following administration of a single 50 mg dose of EPAG. The degree of hepatic impairment was based on Child-Pugh score. Plasma EPAG AUC0- $\infty$  was 41% higher in subjects with mild hepatic impairment, and 80% to 93% higher in subjects with moderate to severe hepatic impairment compared with healthy subjects.

## 10.3.2. Related to bone marrow aspirate and biopsy

No major risks are involved with bone marrow aspirate and biopsy. However, a small risk of infections, pain, bleeding, and hematoma formation at the site of the aspiration exists with the procedure.

## 10.3.3. Related to blood draws

No major risks are involved with blood draws. Minor complications including bleeding, pain, and hematoma formation at the site of blood draws. Infections may rarely occur.

10.3.4. Related to neurodevelopmental testing

The only anticipated adverse consequences associated with neurodevelopmental testing will be the time required for the participants to complete the assessment.

## 10.3.5. Related to HRQL

The only anticipated adverse consequences associated with the HRQL will be the time required for the participants to complete the questionnaire.

## 10.3.6. Related to MRI imaging

MRI imaging may cause discomfort to patients, especially patients with claustrophobia. Anxiolytics will be provided to patients to relieve this discomfort. For pediatric patients and severely affected adults, it may be necessary to provide sedation. There is no risk of allergic reaction in patients with a positive history as contrast (intravenous or oral) is not planned for these studies. There is a risk of burns or injury if metal is present in the scanner; patients will be pre-screened prior to all scans.

## 10.3.7. Risks related to genetic testing

Accidental disclosure of genetic information derived from research testing will be unlikely as all samples and research data will be coded and kept separately from the patient demographic information. Individually identifiable genetic data directly related to this study will not be released to participants. We do not intend to report mutations in genes associated with disease risk that are incidental to our research aims, commonly referred to as "incidental findings." With increasing technology, it is possible that a person may be identifiable from their sequence data submitted as part of a publication of this material. We will attempt to limit this, by again using only coded specimens.

## 10.4. Risks in Relation to Benefit

## 10.4.1. For adult subjects

The benefits to the patients could be improvement of cytopenias (increased blood cell numbers) and/or reduction or even abolition of transfusion requirements, resulting in improved quality of life and also decreased morbidity and mortality from transfusion-associated viral agents, and/or a susceptibility to infections. Potentially, treatment with other more toxic therapies could also be avoided or postponed.

## 10.4.2. For children

The inclusion of children satisfies the criteria set forth in 45 Code of Federal Regulations 46, Subpart D: 46.405 as follows:

- (a) the risk is justified by the anticipated benefit to the subjects: We are offering pediatric subjects, with a probably lethal hematological disease, an alternative to symptomatic therapy.
- (b) the relation of the anticipated benefit to the risk is at least as favorable to the subjects as that presented by available alternative approaches. The benefits to the patients could be reduction or even abolition of transfusion requirements and/or improvement of low peripheral blood counts, resulting in improved quality of life and also decreased morbidity and mortality from transfusion-associated viral agents, iron overload, and/or a susceptibility to infections. Potentially, treatment with other more toxic therapies could also be avoided or postponed.
- (c) adequate provisions are made for soliciting the assent of the children and permission of their parents or guardians, as set forth in 46.408.

## 10.4.3. For Cognitively Impaired subjects

This research provides the prospect of direct benefit; therefore, inclusion is justified. The benefits to the participants could be improvement of anemia resulting in improved quality of life and also decreased morbidity and mortality from transfusion-associated viral agents, iron overload, and/or a susceptibility to infections. Potentially, treatment with other more toxic therapies could also be avoided or postponed. Not allowing participants who cannot provide consent would deny them these potential benefits this protocol offers. There are no plans to include institutionalized participants. There are no known additional risks specific to this group that would not apply to other groups of participants.

10.5. Informed Consent Processes and Procedures

Informed consent will be conducted following OHSRP Policy 301- Informed Consent.

An IRB-approved consent form will be provided to the participant electronically or by hard copy for review prior to consenting. The initial consent process as well as re-consent, when required, may take place in person or remotely (e.g., via telephone or other NIH approved platforms). The investigational nature and objectives of this trial, the procedures, and their attendant risks and discomforts and potential benefits will be carefully explained to the participant in a private setting. The participant will be given as much time as they need to review the document and to consult with their family, friends, and personal health care providers. In addition, a study team member will be available to answer any questions.

A signed and dated informed consent document will be obtained by any investigator authorized to consent prior to entry onto the study. Consent may be obtained with required signatures on the

hard copy of the consent or on the electronic document.

When a document that is in electronic format is used for obtaining consent, this study will use the iMed platform which is 21 CFR, Part 11 compliant, to obtain the required signatures.

During the consent process, participants and investigators may view the same approved consent document simultaneously when participant is being consented in person at the Clinical Center or both will view individual copies of the approved consent document on screens in their respective locations remotely. Signatures may be obtained either by both directly signing on the device that the consenting investigator is using (when in person) or through iMed Mobile Signature Capture (remotely) which allows texting or emailing a link to the participant. That link allows the participant to review the consent, then proceed to sign on the device they are using.

Whether hard copy or electronic, both the investigator and the participant will sign the document with a hand signature using a pen (if using hard copy), finger, stylus, or mouse (if electronic).

When done remotely, if the participant prefers to sign a hard copy, they may be instructed to sign and date the consent document during the discussion and mail, secure email or fax the signed document to the consenting investigator.

Whether in person or remotely, the privacy of the participant will be maintained.

Finally, the fully signed informed consent document will be stored in the electronic medical record, and the participant will receive a copy of the signed informed consent document.

**Subjects who are cognitively impaired and who lack capacity to provide consent:** The consent process for these subjects will follow the requirements of Policy 403.

*Procedures to determine capacity:* If documentation of decision-making capacity is not present in the medical record or the investigator questions the decision-making capacity of the individual, then the Ability to Consent Assessment Team (ACAT) [contact] or [contact]) will be contacted to make the determination.

*Justification for inclusion:* This research provides the prospect of direct benefit; therefore, inclusion is justified. There are no plans to include institutionalized participants.

*Procedures to obtain assent and documentation of assent or dissent:* The informed consent discussion will include the individual unable to provide informed consent along with LAR. The individual unable to provide informed consent will be asked if they agree to participate in the research and this will be documented in the medical record.

**Minor Participants:** If the subject is a minor, the parent who signs the consent for the minor must be a legally authorized parent or guardian. For minors that are age 7 and up, where deemed appropriate by the clinician, and the child's parent or guardian, the child will also be included in all discussions about the trial. Age-appropriate language will be used to describe the procedures and tests involved in this study, along with the risks, discomforts and benefits of participation. Verbal assent will be obtained as appropriate for children less than 12 years of age, exclusive. Children under the age of 18, but who are 12 years of age or older will be asked to sign an ageappropriate assent form. Children under the age of 7 years, exclusive, will not be required to provide assent as they typically do not have the ability to fully understand the nature of research. The consent/assent process will be documented in the child's medical record, including the assessment of the child's ability to provide assent (verbal versus written) as applicable. The parent or guardian will sign on the designated line on the informed consent attesting to the fact that the child had given assent. All children will be reconsented upon reaching the age of 12 years, as described below. For pediatric patients with cognitive disabilities, the requirement for assent, written and/or verbal, will be adjusted as deemed appropriate by the clinician and the child's parent(s) and/or guardian(s).

In cases where parents share joint legal custody in making medical decisions of their child (e.g. by a custody agreement or court order) both parents must give their parental permissions regardless of level of risk of the research. Exceptions may be made if one parent is deceased, becomes incompetent or is not reasonably available (e.g. in prison).

If the minor subject is a female of childbearing age, she will be informed about pregnancy testing and will be told that if her pregnancy test is positive, we will counsel her and help her tell her parents or we will tell her parents. If she does not agree she will be advised not to sign the assent.

**Minors when they reach the age of majority:** When a pediatric subject reaches age 18, continued participation will require consenting of the now adult subject with the standard protocol consent document to ensure legally effective informed consent has been obtained. Should sample or data analysis continue following completion of active participation and the subject has reached 18 years of age, we will attempt to contact the subject using the last known contact information to obtain consent for continued use of data or samples collected during their prior visit. Given the length of time that may have transpired for some of the subjects since their last visit for this study, we request waiver of informed consent for those individuals who after good faith efforts, we are unable to contact.

The consent process for cognitively impaired minor subjects who reach the age of majority will follow the requirements of Policy 403.

Requirements for Waiver of Consent consistent with 45 CFR 46.116 (f)(3), each of which must be addressed in relation to the protocol:

(1) The research involves no more than minimal risk to the subjects

- a. Analysis of samples and data from this study involves no additional risks to subjects.
- (2) The waiver or alteration will not adversely affect the rights and welfare of the subjects
  - a. Samples and data will be kept in secure locations in the laboratory of [name] under the supervision of [name]. Retention of samples or data does not affect the welfare of subjects.
- (3) The research could not practicably be carried out without the waiver or alteration
  - a. Considering the length of time between a minor's enrollment and their age of majority, it is possible that more than a few subjects may be lost to follow up. A significant reduction in the number of samples analyzed could impact the quality of the research.
- (4) Whenever appropriate, the subjects will be provided with additional pertinent information after participation.
  - a. We only plan to request a waiver of reconsent for those subjects who have been lost to follow-up.

## 10.6. Conflict of Interest

The Principal Investigator assured that each associate investigator listed on the protocol title page received a copy of the NIH's Guide to preventing conflict of interest. Investigators added subsequent to the initial circulation were provided a copy of the document when they were added. Copies of the Conflict of Interest Statement were forwarded to FDA and to the NHLBI Clinical Director.

## 10.7. Collaborative Agreements

Cooperative Research and Development Agreement (CRADA)

This protocol has an associated CRADA with Novartis.

Material Transfer Agreements (MTA)

Between NHLBI ([name], Ph.D.) and [name] at University of Washington. Upon execution of the MTA, coded peripheral blood or marrow samples from 20H0021 may be sent to the University of Washington. The goal of this collaboration is to identify the defect in red blood cell development for each patient, matching these results with disease-causing mutation (if known) and drug response, the final goal of which is to understand the underlying cause of response or lack thereof. The NIH research team will receive research results that can be linked to identifiers as part of this research collaboration.

## **11.Pharmaceuticals**

11.1. Eltrombopag (Promacta®)

[figure not shown]
## Supply: Novartis

**Chemical Name:** The chemical name for eltrombopag olamine is 3'-{(2Z)-2-[1-(3,4-dimethylphenyl)-3-methyl-5-oxo-1,5-dihydro-4H-pyrazol-4-ylidene]hydrazino}-2'-hydroxy-3-biphenylcarboxylic acid - 2-aminoethanol (1:2).

Molecular formula: C25H22N4O4.2(C2H7NO).

**Molecular weight** is 564.65 for eltrombopag olamine and 442.5 for eltrombopag free acid.

## Chemical and structural formula:

**Physical form:** red/brown solid.

**Solubility:** Eltrombopag olamine is practically insoluble in aqueous buffer across a pH range of 1 to 7.4, and is sparingly soluble in water.

**Supply:** The drug Novartis is providing for this study may be either investigational or commercial material, based on their supply. It is available as tablets of 12.5, 25, 50 and 75mg. It is also available as a powder for oral suspension (PfOS) that will be available in 12.5 mg or 25 mg strength.

• Tablets:

White, round, film-coated tablets without debossing are provided, containing eltrombopag olamine equivalent to 12.5 mg, 25 mg, 50 mg, or 75 mg of eltrombopag free acid. Placebos to match the active tablets are available. Tablets

are packaged in white HDPE bottles with white plastic, induction-seal, child-resistant caps.

Green, oval, film-coated tablets debossed with 'SLC' on one side are provided, containing eltrombopag olamine equivalent to 200 mg or 300 mg of eltrombopag free acid. A placebo to match the active tablets is available. Tablets are packaged in white HDPE bottles with white plastic, induction-seal, child-resistant caps. Desiccant may be included.

Commercial image actives (12.5 mg - white, 25 mg- orange or white, 50 mg blue or brown, 75 mg – pink, ) which are equivalent to the clinical forms with the exception of the film coated color may also be provided for clinical use. These forms are also packed in white HDPE bottles with white plastic, induction -seal, child-resistant caps. Desiccant may be included. Additionally, the commercial image tablets may be provided in aluminum foil blister packages.

#### • Powder for Oral Suspension:

Doses for children between the ages 4 to 5 (2.5mg/kg non-East/South Asian participants, and 1.25mg/kg East/South Asian participants) will be provided in the form of sachets (when available). The powder for oral suspension is a reddish brown to yellow powder in a sachet. Two PfOS strengths are available, containing eltrombopag olamine equivalent to 12.5 mg and 25 mg of eltrombopag free acid. Reconstitution of eltrombopag PfOS will follow instructions outlined in the Investigator's Brochure and Package Insert.

**Stability:** Store, both tablets and powder, at 25°C (77°F); excursions permitted to 15° to 30°C (59° to 86°F) [*see USP Controlled Room Temperature*].

**Shipping:** The NIH Investigational Drug Management and Research Section (IMDRS) will be responsible for receiving, storing, dispensing and accounting for drug product. The shipping address for Novartis supplied investigational agent is:

National Institutes of Health IMDRS, [name] Shipping Designee Name: [name] Shipping Designee [contact] Shipping Designee [contact] Shipping Designee e-mail: [contact] **Accountability Procedures:** Drug accountability records will be maintained for all clinical supplies. All empty and partially used vials and clinical trial supplies will be destroyed locally according to the institution's standard operating procedures for drug destruction. The pharmacy will maintain detailed documentation of the number and identification of vials, which are destroyed, and copies of these documents will be provided to the Sponsor and Novartis. Disposition of all unused boxes of study drug will be carried out according to instructions provided by the Sponsor and/or Novartis at the end of the study after drug accountability is performed.

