#### 5. Treatment Plan

5.1. Administration of study drug (eltrombopag)

Subjects will initiate EPAG at a starting daily dose as detailed below, according to age and ethnicity. Subjects 12 years of age and above will receive the adult dose of 150 mg. Those between 6 and 11 will start at 75 mg, and children 2 and 5 years of age will start at 2.5 mg/kg, not to exceed 75 mg (Table 1).

To adjust for the higher expected exposure in subjects of East Asian and South East Asian ancestry, the starting dose for East Asian and South East Asian subjects 12 years of age and above will be 75 mg once daily. For East Asian and South East Asian subjects between 6 and 11 years of age, the starting dose will be 37.5 mg once daily, and for children between 2 and 5, the starting dose will be 1.25 mg/kg (Table 1).

Age group Daily dose		
	Non-Asian	
≥12	150 mg	
6-11	75 mg	
2-5	2.5 mg/kg, max 75 mg	
East Asian, South East Asian		
≥12	75 mg	
6-11	37.5 mg	
2-5	1.25 mg/kg, max 37.5 mg	

Table 1: Starting daily dose of eltrombopag according to age and ethnicity

Eltrombopag dose may be interrupted when clinically indicated at the discretion of the investigator. If EPAG dosing is delayed or interrupted for more than 1 week (7 days) and the interruption is not the result of a severe adverse event related to EPAG, then the subject will receive EPAG for additional time in order to receive a total of 24 weeks as originally planned. Interruptions shall be recorded in the medical record. Whether interruptions are reported (e.g. as deviations or adverse events) shall be determined as per Policy 801.

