# **10.Human Subject Protection**

# 10.1. Rationale for subject selection

With an incidence of about seven cases per million live births each year in the US and with a 50-60% expected rate of refractory disease and/or failed first-line therapy, DBA constitutes a rare disease (18). The study will be open to all subjects who satisfy the inclusion criteria and provide an informed consent to the protocol, or have a guardian authorized to provide consent on their behalf. No subjects will be excluded from participation based on gender, race or ethnicity.

**For subjects of Asian ethnicity:** Plasma EPAG area under the curve was approximately 70% higher in East and South East Asian (ethnicity self-reported) subjects as compared with non-Asian subjects who were predominantly Caucasian. Therefore, subjects of Asian heritage will be included but they will be initiated at a lower dose and monitored closely as described in the treatment plan.

**For subjects with renal impairment:** The pharmacokinetics of EPAG has been studied in adult patients with renal impairment. Following administration of a single 50 mg dose, there was a trend for reduced plasma EPAG exposure in patients with renal impairment, but there was substantial variability and significant overlap in exposures between patients with renal impairment and

healthy volunteers. Therefore, patients with impaired renal function will be included and given the protocol-defined dosages, but participation will be monitored closely.

**For subjects with hepatic impairment:** Pharmacokinetics of EPAG have been studied in adult patients with hepatic impairment. Following the administration of a single 50 mg dose, the  $AUC_{0-\infty}$  of EPAG was increased by 41% in subjects with mild hepatic impairment and by 80% to 90% in subjects with moderate or severe hepatic impairment compared with healthy volunteers. Therefore, patients with minimally impaired hepatic function will be included but participation will be monitored closely. Patients with baseline moderate to severe hepatic impairment will be excluded from the study.

**Recruitment efforts:** The study may use the following strategies of recruitment including:

- ClinicalTrials.gov website
- Clinical Center Research Studies ("Search the Studies") website
- Diamond-Blackfan Anemia Foundation, Inc. (dbafoundation.org) website
- National Heart, Lung and Blood Institute (NHLBI) patient recruitment website
- Twitter messages and chats with study investigators

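### Sections 5.1 and 11.1 give a South Asian child aged 4 to 5 two starting doses that differ two-fold, and no formulation is assigned to ages 2 to 3

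*Combined protocol and SAP*

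**What the plan says.** **Section 5.1, text.** The default rules are set by age alone. For the oldest band: "Subjects 12 years of age and above will receive the adult dose of 150 mg". For the youngest: "children 2 and 5 years of age will start at 2.5 mg/kg, not to exceed 75 mg". An exception by ancestry follows: "the starting dose for East Asian and South East Asian subjects 12 years of age and above will be 75 mg once daily". For the same two ancestry groups at ages 6 to 11, "the starting dose will be 37.5 mg once daily" (default 75 mg), and "for children between 2 and 5, the starting dose will be 1.25 mg/kg".

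**Tables 1 and 3.** The starting-dose table and the taper table each have two blocks of rows, one labelled Non-Asian and the other East Asian, South East Asian. Table 1 caps the two weight-based doses at 75 mg and 37.5 mg.

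**Section 11.1, Powder for Oral Suspension.** "Doses for children between the ages 4 to 5 (2.5mg/kg non-East/South Asian participants, and 1.25mg/kg East/South Asian participants"), to be supplied as sachets when these are available.

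**Section 10.1.** After citing exposure data for East and South East Asian subjects, it concludes that "subjects of Asian heritage will be included but they will be initiated at a lower dose and monitored closely as described in the treatment plan".

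**Section 2.4.4.** The pediatric rationale applies the full 2.5 mg/kg start (ages 2 to 5) and the full 75 mg start (ages 6 to 11) to non-East-Asian subjects.

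**Section 4.1.** Enrolment opens at 2 years of age and 12 kg.

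**The concern.** Sections 5.1 and 11.1 both attach a mg/kg figure to an ancestry group, and the groups are not the same. South Asian subjects fall on the full-dose side in 5.1 and on the reduced-dose side in 11.1. These subjects are eligible, since Section 10.1 states that nobody is excluded on race or ethnicity.

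The protocol treats ancestry as relevant to exposure. Sections 2.4.3, 10.1 and 10.3.1 put plasma levels about 70% higher in East and South East Asian patients, and none of them gives a figure for South Asian subjects. Section 2.4.4 also reports about 60% higher exposure at ages 1 to 5 than in adults. The children caught by the conflict are therefore in an age group that the protocol already marks as more exposed.

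What is at stake is which starting dose a particular child receives, and whether the treatment plan and the pharmaceutical section lead to the same answer. A wrong assignment would not be picked up early from drug levels, because pharmacokinetic sampling is placed only at the 6-month visit (Section 6.4, Appendix B).

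**Working it through.** The plan states no figure to reproduce here. The check sets the passages side by side and takes the dose ratios.

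**1. Who gets the reduced start, as written**

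| Place | Reduced start | Full start | South Asian subject |
|---|---|---|---|
| 5.1 text | East Asian, South East Asian | all others, by default | full |
| Tables 1 and 3 | East Asian, South East Asian | Non-Asian | in neither block |
| 11.1 (ages 4 to 5) | East/South Asian | non-East/South Asian | reduced |
| 10.1 (no ages) | Asian heritage, as in the treatment plan | not stated | unclear; defers to Section 5 |
| 2.4.4 (rationale) | not stated | non-East-Asian | full |

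Only 5.1 with its tables and 11.1 give doses by ancestry for the trial's conduct. These are the two places that collide. The label in 2.4.4 has a further oddity: read literally, it puts South East Asian children on the full start, which 5.1 does not.

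**2. Size of the difference where 5.1 and 11.1 collide (ages 4 to 5)**

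Ratio = full dose / reduced dose = 2.5 / 1.25 = 2.0.

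The caps in Table 1 do not change this, because both bind at the same weight: 75 / 2.5 = 30 kg and 37.5 / 1.25 = 30 kg.

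- At 12 kg, the minimum weight: 2.5 × 12 = 30 mg against 1.25 × 12 = 15 mg, ratio 2.0.
- At 20 kg: 50 mg against 25 mg, ratio 2.0.
- At 30 kg and above: 75 mg against 37.5 mg, ratio 2.0.

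**3. Other ages**

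The full and reduced doses also stand at 2 to 1 in the other bands of Table 1 (150 / 75 mg and 75 / 37.5 mg). Section 11.1 gives no ancestry-based dose outside ages 4 to 5, so it sets up no second dose there. For a South Asian subject of any other age, the 5.1 text gives one answer and only the table labels fail to match it.

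**4. Age range and formulation**

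- Enrolment: from age 2 (Section 4.1).
- Weight-based dosing: ages 2 to 5 (5.1, Table 1, 2.4.4).
- Sachets assigned: ages 4 to 5 (11.1).
- Left without an assigned formulation: ages 2 to 3.

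This gap matters in practice. The tablet strengths listed in 11.1 (12.5, 25, 50 and 75 mg) are all multiples of 12.5 mg, and 30 / 12.5 = 2.4 and 15 / 12.5 = 1.2. Whole tablets therefore cannot make up either calculated dose for a 12 kg child. The general supply paragraph of 11.1 does list the powder without an age limit.

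**The case against.** The best case for the plan has four parts.

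- **Section 5.1 governs and is complete.** It sets a start by age for everyone and then carves out two ancestry groups. Section 2.4.3 and Table 3 name the same reduced-dose groups. On this view 11.1 is a product description with a loose abbreviation for East and South East Asian. This is plausible, but no section says so, and the abbreviation names a different population. It stands as a reason to expect an easy reconciliation, not as a resolution.
- **Section 10.1 is not a rival rule.** A reader might infer that it gives the lower dose to everyone of Asian heritage, which would extend the two-fold conflict to every age band. The documents do not support that. The sentence follows from data on East and South East Asian subjects, states no ages or doses, and refers to the treatment plan. This part of the objection stands in full.
- **Nobody is without a dose, and ages 2 to 3 are not without supply.** A reader might infer either from Table 1 or from 11.1. The 5.1 default text assigns every subject a starting dose, and powder is listed with no age limit. This also stands: the gap at ages 2 to 3 is an unassigned formulation.
- **The practical effect may be nil.** The trial has one site and one NIH section dispensing the drug, and the documents give no basis for the number of South Asian children aged 4 to 5 who might enrol; it could be zero. This stands against any claim of a measurable effect on the results. It does not remove the contradiction for the first such child.

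**Conclusion.** The plan contradicts itself on an operative dosing rule, within narrow limits. For South Asian children aged 4 to 5, Sections 5.1 and 11.1 give starting doses of 2.5 and 1.25 mg/kg, a ratio of 2.0 at every weight from the 12 kg minimum upward. This rests on reading the Section 11.1 label as written; if the sponsor confirms that it was meant as shorthand for East and South East Asian, the conflict disappears once the wording is corrected.

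Two lesser defects go with it. The ancestry labels in Tables 1 and 3 do not cover South Asian subjects at any age, although the 5.1 text does. The labels in 2.4.4 and 10.1 add ambiguity without being dosing rules of their own. Separately, children aged 2 to 3 have a defined dose but no assigned formulation.

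The point should be corrected because it concerns the dose given to young children. Each subject is 1 / 25 = 4% of the planned sample, but the number affected is unknown and may be zero, so no effect on the response or safety analysis is claimed. The two-stage design, its alpha and its power do not change.

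**What to change.** Reconcile Sections 2.4.4, 5.1, 10.1 and 11.1 and Tables 1 and 3:

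1. Define the ancestry groups once, including how self-report is mapped to a group, and use the same labels everywhere. Every eligible subject should fall in exactly one row of Table 1 and the matching row of Table 3.
2. Use one age range for the weight-based band in 5.1, 2.4.4 and 11.1, and assign a formulation to every age in it, including 2 to 3.
3. Have 11.1 refer to Table 1 for doses, so that they are stated in one place only.

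Which ancestry group, dose or formulation is right is for the sponsor to decide; none is proposed here. The cost is a wording amendment in these places, with the usual IRB review. No design or analysis element has to be recalculated.
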